1. Pregnant or lactating female (This is an FDA-required exclusion. In the future, if rTMS becomes a proven treatment for major depression, its safety in the context of pregnancy should be studied separately (Nahas et al. 1999).
2. Unable to be safely withdrawn, at least two-weeks prior to treatment commencement, from medications that substantially increase the risk of having

seizures. For the purpose of this study, those medications are listed in Appendix H (for example, theophylline).

3. Have a cardiac pacemaker.
4. Have an implanted device (deep brain stimulation) or metal in the brain.
5. Have a cochlear implant.
6. Have a mass lesion, cerebral infarct, increased intracranial pressure, or other active CNS disease, including a seizure disorder.
7. Known current psychosis as determined by DSM-IV or SCID (axis I, psychotic disorder, schizophrenia) or a history of a non-mood psychotic disorder.
8. Known current Bipolar I disorder as determined by SCID or a History of Bipolar I disorder.
9. Current amnestic disorders, dementia, BOMC > 10, delirium, or other cognitive disorders.
10. Current substance abuse (not including caffeine or nicotine) as determined by positive toxicology screen, or by history via SCID, within 3 months prior to screening.
11. Patients with an elevated risk of seizure due to TBI.
12. Participation in another concurrent clinical trial.
13. Patients with prior exposure to rTMS.
14. Active current suicidal intent or plan as evidenced by a score of 4 or 5 on the suicidal ideation portion of the CSSRS or the endorsement of an actual attempt, interrupted attempt, or an aborted attempt in the past 6 months. All patients will be required to establish a written safety plan involving their primary VA psychiatrist and the treatment team before entering the clinical trial (See Section X.B.8).
15. Unstable cardiac disease or recent (< 3 months previous) myocardial infarction.
16. Patient refuses to sign consent for participation in the study.

VI. METHODOLOGY

A. Recruitment

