5. Minorities and Women: Because the VA population is largely male, the proportion of females enrolled will not be representative of actual prevalence rates. Although most recruitment will occur in mental health clinics, recruitment within women’s health clinics will be used to try to maximize the enrollment of eligible women. Ethnic and racial minorities are well-represented in the VA population and study staff will be trained to recognize the variations in symptom presentation characteristic of ethnic and racial minorities so that potential participants from these groups will not be excluded.

B. Screening Assessments

Patients who are screened for possible eligibility for the study will be listed on the Patient Screening Log. After the patient signs the Informed Consent Form, the screening procedures and assessments can be initiated. A template of the Informed Consent Form can be found in Appendix A. The screening phase will last between two and four weeks to allow adequate time for all of the assessments to be completed, to assure the patient's capacity and willingness to participate in the study and to ensure that all patients have HRSD24 scores above entry criteria for the study within seven days prior to randomization. If the SI feels that the patient may not be capable of giving informed consent, the SI may request a competency evaluation using the VA standard clinical protocol. All assessments and their frequencies of administration are listed in Table 2 in Protocol section VI.G. Although screening data will not be used in the primary analysis, it will be retained to determine if participants who entered the study were comparable to those who were excluded.

C. Randomization to Treatment

Patients who sign the Informed Consent Form and meet the study eligibility criteria will be enrolled into the study and will be randomized into one of 2 treatment groups: rTMS or sham rTMS. Patients who fail screening may be re-screened at a later time at the discretion of the site investigator.

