To randomize a patient into the study, the SI or the SC will submit the electronic randomization form. This computerized system, after verifying eligibility, will randomize a patient to either the rTMS or to the sham rTMS treatment group. A non-sequential treatment number will be assigned. This unique treatment number will be key entered into the device which will be associated with a treatment assignment and will enable the rTMS device to deliver the appropriate treatment (active or sham) to each patient. Every attempt will be made to randomize a participant so that he/she will receive his/her first rTMS treatment as soon as possible after randomization. Non-sequential treatment numbers will be assigned to ensure that investigators cannot initiate a participant on treatment before randomization. An adaptive randomization scheme will be used so that approximately equal numbers of patients will be randomized to each treatment group within several important subsets. These subsets include patients with a substance abuse disorder and patients with PTSD. Enrolling site will also be

incorporated into the adaptive randomization scheme. A “biased coin” procedure will be used to make an assignment that will improve overall balance more likely than an assignment that will not (Efron 1971). Imbalance will be calculated by summing the marginal totals for these three factors for each treatment group and calculating the difference, D. If the imbalance is less than three, assignments will be made with equal probability; otherwise, the probability of assigning to the group that will increase imbalance will be $1/D$. This approach will be incorporated within the electronic data capture system.

D. Duration of the Study

The duration of the study will be three and a half years, with a three year enrollment period. Each participant will be in the trial for a total of approximately 29-39 weeks (2-4 weeks screening, 4-11 weeks acute treatment phase and 24 week follow-up phase).

E. Intervention Procedure

The overview of the experimental design and procedures is presented in Figure 2.

[figure not shown]

Figure 2: Overview of Research Design

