Units of 5 sessions will normally be delivered over one week’s time. As is the case with other somatic treatments such as electroconvulsive therapy, some consideration of scheduling flexibility must be made to accommodate holidays and other events. These units of 5 sessions can be delivered over a minimum of 5 calendar days and should be delivered within 12 calendar days. Thus, the entire acute treatment phase would normally take between 4 weeks to 11 weeks. At the end of each treatment block, study staff will enter progress notes for each participant in CPRS. These progress notes will be very brief in nature and contain no results or scores of assessments and will serve simply as records of treatment and assessment. The participant’s primary mental health provider will be listed as an additional signer on these

CSP #556 “The Effectiveness of rTMS in Depressed VA Patients”

Version 4.6, February 2016

Main Section of Protocol

notes. This is to ensure that providers are aware of the veterans progress throughout the study and to maintain an open line of communication with study staff.

Follow-up Phase. After the acute treatment phase ends, all patients will enter a 24 week follow-up period. Taper treatments are considered part of the Follow-up Phase. Follow-up visits will occur approximately monthly during the follow-up phase. These visits should be face-to-face but, in unusual circumstances, telephonic visits may be allowed. Appropriate assessments to measure treatment effects after the acute and follow-up phases will be collected as described in Table 2, Assessments and Frequencies of Administration, in Protocol section VI.G. At the end of each follow-up visit, study staff will enter progress notes for each participant in CPRS. These progress notes will be very brief in nature and contain no results or scores of assessments and serve simply as records of assessment. As on the notes in the acute phase, the participant's primary mental health provider will be listed as an additional signer on these notes.

F. Treatment Regimen

1. Rationale for Selection of rTMS Stimulation Parameters

The Planning Committee's decision regarding the choice of rTMS stimulation parameters in this trial was made in a systematic way with data from three sources.

- a. First, the Planning Committee members performed a thorough literature review of the rTMS antidepressant trials performed over the last 15 years (n=70 trials as of 12/06).

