			Screening/ Baseline	5	10	15	20	[25]	[30/ last]	1	2	3	4	8	12	16	20	24
86	Consent	S*																
01	Screening Form	S																
02	Randomization Form	B*																
03	Baseline	S																
04	Medical History	S																
05	Physical Exam	S							x									
06	Labs	S																
07	Structured Clinical Interview for DSM-IV-TR (SCID-I)	S																
08	Current/Past ATHF	S																
09	Lifetime Drinking History	B																
10	Clinician Administered PTSD Scale (CAPS)	B							x									x
11	Trauma History Questionnaire (THQ)	B																
12	Life Stressor Checklist-revised (LSC-R)	B																
13	Six-Item Blessed Orientation-Memory-Concentration (BOMC)	S																
14	Pregnancy Test	S ²	Every 4 weeks															
15	Medication Use	S	x	x	x	x	x	x	x	x	x	x	x	x	x	x	x	
16	Study Visit Form		x	x	x	x	x	x	x	x	x	x	x	x	x	x	x	
17	Audiometry: REMOVED																	
18	rTMS Treatment Log		x	x	x	x	x	x	x									
19	rTMS Taper Log									x	x	x						
20	Hamilton Rating Scale for Depression (HRSD) and MADRS	S ²	x	x	x	x	x	x	x				x	x	x	x	x	x
21	Beck Depression Inventory (BDI)	B	x	x	x	x	x	x	x				x	x	x	x	x	x
22	Quick Inventory of Depressive Symptomatology (QIDS-C16)	B	x	x	x	x	x	x	x				x	x	x	x	x	x
23	Columbia-Suicide Severity Rating Scale (C-SSRS)	S																
24	Columbia-Suicide Severity Rating Scale (C-SSRS) F/U		x	x	x	x	x	x	x	x	x	x	x	x	x	x	x	x
25	Beck Scale for Suicidal Ideation (BSS)	S	x	x	x	x	x	x	x	x	x	x	x	x	x	x	x	x
26	Beck Hopelessness Scale	S	x	x	x	x	x	x	x	x	x	x	x	x	x	x	x	x
27	Quality of Life (VR 36)	B							x									x

Assessment		Screening/ Baseline	Acute Treatment Phase						Follow-up Phase								
			4 - 11 weeks						24 weeks (6 months)								
			2-4 weeks		End of Session Number ¹				PRN Taper weeks		Weeks						
			5	10	15	20	[25]	[30/ last]	1	2	3	4	8	12	16	20	24
28	Neuropsychological Battery	B						x									x
29	DAST	S						x									x
30	PTSD Checklist (PCL)	B						x									x
31	MAST	S						x									x
32	STAXI-2	S	x	x	x	x	x	x	x	x	x	x	x	x	x	x	x
TLFB	Alcohol/Drug Timeline Followback (TLFB)		x	x	x	x	x	x	x	x	x	x	x	x	x	x	x
33	Urine Tox Screen/Alcohol Test	S		x		x		X		x		x	x	x		x	
34	Termination Form ³																x
35	Control Questionnaire	Before and after the 1 st treatment															x
36	Protocol Deviation	As required															
37	Adverse Events (AE) and ADE and Serious Adverse Events (SAEs) and UADE	As required															

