***B= Baseline**

***S= Screening**

¹ Sessions 21-25 and 26-30 may not be required if patient goes into remission earlier

² Must be conducted within 7 days prior to randomization

³ Termination Form will be completed at the end of the study OR when a patient decides to end study participation prior to the study completion date; i.e., a patient decides to withdraw or leave the study for any reason, withdraws consent, or is suspended from the study.

1. Demographics, Medical History, Physical Exam, Laboratory, Toxicology, Pregnancy

Test and Medication Use. Relevant demographics will be collected as to age, gender, racial/ethnic grouping, military history and income. In addition, a standard Medical History and Physical Exam will be completed as well as laboratory tests including a Complete Blood Count (CBC), electrolytes (chemistry), thyroid panel and a liver function test. An alcohol test and urine drug toxicology screen will be conducted prior to randomization and also randomly during the following time points of study participation:

- Acute Treatment Phase: 2nd, 4th, and 6th (if still in acute treatment) weeks
- Taper Phase: 2nd week
- Follow-up Phase: 1st, 3rd, and 5th months

A pregnancy test will be conducted on all female patients of childbearing potential (that is, all women except for those who are post menopause for > 2 years or who have a history of hysterectomy or surgical sterilization) prior to randomization and every four weeks during the study. Information on medication use (prescription, natural food products, and “over the counter”) will be collected at screening and updated after each block of five sessions during the treatment phase and every four weeks during the follow-up phase.

2. Structured Clinical Interview for DSM-IV (SCID) (First et al., 2002). The Structured Clinical Interview for DSM-IV Axis I Disorders (SCID) is a semi-structured interview that is used to make the major DSM-IV Axis I diagnoses in the most uniform manner possible.

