15. Quick Inventory of Depressive Symptomatology (QIDS-C16). The ACNP recommends that outcome measures reflect all major criteria used in the diagnosis of MDD. For that reason the Planning Committee recommended additional use of the Quick Inventory of Depressive Symptomatology (QIDS-C16), which meets the ACNP criteria (Rush et al., 2003). The HRSD does not measure hypersomnia, weight gain or problems with concentration or decision making.

16. Columbia – Suicide Severity Rating Scale (C-SSRS). Suicide is a rare event. As such, suicide rates cannot be used as an outcome measure for an rTMS study. Similarly, the study is of too short a duration to expect to find a significant difference in numbers or lethality of suicide attempts between treatment and placebo (sham rTMS) groups. Nonetheless, there are two areas that can be expected to change with successful rTMS treatment: preoccupation with suicidal ideations or plans. Because this study uses both a lead in period prior to treatment and a sham rTMS treatment group, we will be able to compare the rate of parasuicidal behavior in these patients, who are at more serious risk of a suicide completion. One of the newer methods of monitoring patients at risk for suicide is the C-SSRS. The C-SSRS assesses suicidal ideation as well suicidal behavior over a specified time period and is frequently employed by the Food and Drug Administration in research to determine if suicidality is an adverse effect. The form will be collected at multiple timepoints in during the course of the study. Initially, it will be collected at baseline to serve as a screener for persons reporting suicidal ideation or behaviors in the past six months. It will also be completed weekly during acute treatment and then monthly during the follow-up phase to monitor for the presence of suicidal ideation or behaviors. The sensitivity of this instrument will allow us to identify even “minor” suicide “gestures” as well as more serious attempts.

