COMPLETE AT RANDOMIZATION ONLY

1. Please enter this participant's 5-digit participant number _____
2. Please enter this participant's four character Alpha Code _____
3. Was a Safety Plan created for this subject? (*circle one*) No Yes
4. Please provide the date of the most recent HRSD assessment? ____/____/____ _{MM} _{DD} _{YYYY}
Note that the HRSD assessment date cannot exceed 7 days prior to randomization.
5. Please enter this subject's 2-digit HRSD score ____
6. If female, and of child bearing potential, please provide date of most recent pregnancy test
____/____/____ _{MM} _{DD} _{YYYY}
7. Does this subject have a history of substance abuse? (*circle one*) No Yes
8. Has this subject been diagnosed with PTSD? (*circle one*) No Yes
9. Date randomized ____/____/____ _{MM} _{DD} _{YYYY}
10. Randomized treatment number assigned by Perry Point _____

VA COOPERATIVE STUDY #556

The Effectiveness of rTMS in Depressed VA Patients

Site ____ Participant # _____ Alpha Code _____ Date ____ / ____ / ____
MM DD YYYY

Form 03 – BASELINE INFORMATION

COMPLETE AT SCREENING ONLY

A. PARTICIPANT PROFILE

4. Race (Circle one answer for each category)			
American Indian or Alaska Native	No	Yes	Not Collected
Asian	No	Yes	Not Collected
Black or African-American.....	No	Yes	Not Collected
Native Hawaiian or Other Pacific Islander.....	No	Yes	Not Collected
White	No	Yes	Not Collected
Refused/unknown	No	Yes	Not Collected

5. Current Marital status (*Circle one answer that applies*)

1. Single	5. Separated
2. Married	6. Living with partner
3. Widowed	7. Not Collected
4. Divorced	

6. Highest Degree or Certification (*Circle one answer that applies*)

1. None	5. Associate Degree	9. MD, PhD, Law, Dental
2. GED	6. RN Diploma	10. Other (Specify) _____
3. H. S. Diploma	7. Bachelor's Degree	11. Not Collected
4. Voc Tech Diploma	8. Master's Degree	

B. MILITARY HISTORY

7. When did the participant serve? (*Circle one answer for each below*)

a. World War I	No	Yes	Not Collected
b. World War II	No	Yes	Not Collected
c. Korean conflict	No	Yes	Not Collected
d. Vietnam conflict	No	Yes	Not Collected
e. Gulf War	No	Yes	Not Collected
f. Balkans conflict	No	Yes	Not Collected
g. Afghanistan conflict	No	Yes	Not Collected
h. Iraq conflict.....	No	Yes	Not Collected
i. Other war/conflict:	No	Yes	Not Collected
specify _____			
j. Peace time	No	Yes	Not Collected

8. Did the participant serve outside the United States? (*Circle one*) No Yes

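### The C-SSRS that evidences exclusion 14 has no 7-day limit in Table 2, so it can be up to 28 days old at randomisation, and it is not repeated until the end of session 5

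*Protocol*

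**What the plan says.** Protocol section V.B, item 14, excludes patients with current suicidal intent or plan, shown by a score of 4 or 5 on the ideation part of the C-SSRS, or "the endorsement of an actual attempt, interrupted attempt, or an aborted attempt in the past 6 months". Section VI.G.16 describes the first administration: "Initially, it will be collected at baseline to serve as a screener for persons reporting suicidal ideation or behaviors in the past six months". It then schedules the scale weekly in acute treatment and monthly in follow-up.

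On timing, section VI.B states: "The screening phase will last between two and four weeks". In Table 2 (section VI.G), the screening C-SSRS (row 23) is marked with a plain S. The follow-up version, "Columbia-Suicide Severity Rating Scale (C-SSRS) F/U" (row 24), has no entry in the screening/baseline column and first appears at the end of session 5. Footnote 2, "Must be conducted within 7 days prior to randomization", is attached to the pregnancy test (row 14) and to the HRSD and MADRS (row 20) only.

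The Randomization Form (Appendix E, Form 02) enforces the HRSD limit: "Note that the HRSD assessment date cannot exceed 7 days prior to randomization". It also asks for the pregnancy test date and whether a safety plan exists. It has no C-SSRS item.

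**The concern.** Part of exclusion 14 concerns a current state and part concerns a six-month period. Both should hold when the patient is randomised. The protocol applies this reasoning to the HRSD, which must be above the entry threshold within 7 days of randomisation, but sets no such limit for the C-SSRS.

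A patient who forms intent or a plan, or makes an attempt, after the screening C-SSRS meets exclusion 14. That patient could still be randomised if no other safeguard picks it up. What is at stake is safety at entry and, secondarily, the quality of the pre-treatment suicidality baseline. Section X.B.8 reads the behaviour items of the acute-phase C-SSRS as covering the time since the last assessment. An old screening rating therefore means that the first on-treatment rating reaches back over pre-treatment days.

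**Working it through.** The protocol states no figure for the age of the C-SSRS at randomisation, so there is none to reproduce. The check is a reading of the schedule followed by day counts.

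**Is the missing limit real?** It could be a superscript lost from the table, but that is unlikely. The superscript is present on rows 14 and 20, and both of those limits are repeated elsewhere: the HRSD limit in inclusion criterion 3 and on Form 02, and the pregnancy-test limit on Form 03, item 27. Nothing in the protocol or the forms shown gives a limit for the C-SSRS. Sections VI.G.16 and X.B.8 say baseline where Table 2 says screening, and neither word sets a date.

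**Inputs**
- Screening length s: 14 to 28 days (section VI.B).
- Length of the first five-session block b: 5 to 12 days. Section VI.E says that blocks "can be delivered over a minimum of 5 calendar days and should be delivered within 12 calendar days".
- Assumptions: screening keeps to its stated length, randomisation falls at its end, and treatment starts on the day of randomisation. Any delay before session 1 adds to the gap.

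**Maximum age at randomisation** = s
- Two-week screening: 14 days.
- Four-week screening: 28 days.
- With a 7-day limit: 7 days.

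**Longest gap to the next scheduled C-SSRS** = age at randomisation + b
- Two-week screening: 14 + 5 = 19 to 14 + 12 = 26 days.
- Four-week screening: 28 + 5 = 33 to 28 + 12 = 40 days.
- With a 7-day limit: 7 + 5 = 12 to 7 + 12 = 19 days.

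**Part of the six-month look-back not covered at randomisation** = age / 183, taking six months as 183 days
- 28/183 = 15%.
- 14/183 = 8%.
- 7/183 = 4%.

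These are upper limits. A site that gives the C-SSRS late in screening has a fresher rating, but nothing requires it to do so.

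**What else is dated near randomisation?**

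| Safeguard | Within 7 days? | Re-applies exclusion 14? |
|---|---|---|
| HRSD item 3 (X.B.8) | Yes | No. It triggers a clinical evaluation, and only together with anxiety or agitation items |
| MADRS item 10, score 4 or more (X.B.8) | Yes | No. It triggers a clinical evaluation |
| Beck suicide ideation and hopelessness scales (Table 2, rows 25 and 26) | No, plain S | No |
| Attempts as serious adverse events from consent (VI.H.2) | Continuous | No. It depends on the site learning of the event |
| Form 03, item 41 | Part of the eligibility sign-off | It attests the criterion but calls for no new C-SSRS |
| Safety plan (Form 02) | Confirmed at randomisation | No |

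**The case against.** The strongest reply is that suicidality does not go unwatched in the gap. Form 03 is labelled for completion at screening, but it cannot be finished early. Item 22 asks about medication stability up to randomisation, item 27 requires a pregnancy test within 7 days before it, and item 44 records final eligibility. Item 41, on suicidal intent or plan, belongs to the same sign-off, and a yes makes the patient ineligible. The HRSD and MADRS suicide items are fresh. Section X.B.8 requires immediate evaluation when any scale or the patient's own statements show suicidality. The patient stays under a VA psychiatrist, and attempts must be reported within 72 hours. Most other screening items are also undated, and no passage is contradicted.

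Much of this stands and limits the weight of the point. It does not supply a C-SSRS close to randomisation, which is the evidence that exclusion 14 itself names.

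Three stronger readings are tempting, and the documents do not support them:
- **A count of patients randomised after an attempt in the gap.** The protocol gives no attempt rate. The 6% in section X.B.8 is a threshold for suspending enrolment and not an expected rate, so any count would rest on assumption.
- **That Form 03 ignores past attempts because item 41 does not mention them.** Item 41 repeats the opening words of exclusion 14, under which attempts are listed, and can fairly be read as shorthand for the whole criterion.
- **That the lead-in period in section VI.G.16 is useless as a comparison because eligibility sets prior behaviour to zero.** Exclusion 14 does not bar preparatory acts, so the pre-treatment level need not be zero.

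**Conclusion.** The point holds as a gap in scheduling. The C-SSRS rating behind exclusion 14 can be up to 28 days old at randomisation, against at most 7 for the HRSD, and 33 to 40 days can pass before the next one. The day counts assume a C-SSRS on the first day of a four-week screening and treatment from the day of randomisation; later administration or shorter screening reduces them. The C-SSRS forms (23 and 24) and the operations manual are not shown. A manual might set a window, but the protocol places limits of this kind in Table 2 and sets none there for this scale.

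Other safeguards cover part of the gap, so this should not be read as saying that suicidal patients enter unchecked. It is an improvement worth considering, not an error. It affects safety at entry and the pre-treatment suicidality baseline. The primary endpoint, its analysis, the power and the stopping rules stay as they are.

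**What to change.** Require a C-SSRS within 7 days before randomisation, at the HRSD visit already held in that window. This can be done in either of two ways:
- put footnote 2 on row 23 of Table 2; or
- keep an early screening C-SSRS and add a follow-up C-SSRS (Form 24) in the window for any patient whose first rating is older than 7 days.

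The second keeps the benefit of finding ineligible patients early. In both cases, re-check exclusion 14 at that visit and add the C-SSRS date to Form 02 beside the HRSD date.

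The repeat belongs before randomisation rather than just before session 1. A patient found ineligible after randomisation is already in the intent-to-treat analysis and, if treatment then stops, counts as a failure under section VIII.B.2.

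The cost is one short form for some patients, one added item on Form 02 and one mark in Table 2, with no extra visit. A few patients may fail screening late.
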